6.1. Determination of Sample Size

Study JAHL will aim to enroll approximately 600 patients ≥ 18 years of age. The proposed sample size will ensure a $>90\%$ power to detect any difference between the baricitinib 4-mg and placebo treatment groups and the baricitinib 2-mg and placebo treatment groups, each using a 2-sided alpha of 0.05, assuming 10% placebo, 25% baricitinib 2-mg, and 30% baricitinib 4-mg response rates for the primary endpoint. The assumptions are based on what was observed in the Phase 2 Study (I4V-MC-JAHG). The proposed end point of IGA 0 or 1 represents patients whose AD is clear or almost clear from a baseline of moderate or severe disease. The anticipated effect size represents 3 times more patients achieving this benefit compared to placebo, which in discussion with therapeutic experts, is of a magnitude that is considered clinically relevant.

Sample size and power estimates were obtained from nQuery® Advisor 7.0.

6.2. General Considerations

This plan describes *a priori* statistical analyses for efficacy, health outcomes, and safety that will be performed.

Statistical analysis of this study will be the responsibility of Eli Lilly and Company (Lilly). The statistical analyses will be performed using SAS® Version 9.4 or higher.

Not all displays described in this SAP will necessarily be included in the clinical study report (CSR). Not all displays will necessarily be created as a “static” display. Some may be incorporated into interactive display tools instead of or in addition to a static display. Any display described in this SAP and not included in the CSR will be available upon request.

Statistical tests of treatment effects and confidence intervals (CIs) will be performed at a 2-sided significance level of 0.05, unless otherwise stated (e.g., graphical multiple testing strategy in Section 6.6).

Data collected at early termination visits will be mapped to the closest scheduled visit number for that patient if it falls within the visit window as discussed in Section 6.2.2. For by-visit summaries, only visits in which a measure was scheduled to be collected will be summarized. Any unscheduled visit data will be included at the patient-level listings. However, the data will still be used in other analyses, including shift analyses for safety analytes, change from baseline using modified last observation carried forward (mLOCF) for efficacy analyses, and other categorical analyses including safety.

6.2.1. Analysis Populations

Intent-to-treat (ITT) population: The ITT population analysis set is defined as all randomized patients.

Per-protocol Set (PPS): PP subset of the ITT analysis set will include those patients who do not have any significant or important protocol violations. Qualifications for and identification of

significant or important protocol violations will be determined while the study remains blinded, prior to database lock.

Follow-up population: The follow-up population is defined as patients who entered the follow-up period.

Unless otherwise specified, the efficacy and health outcome analyses will be conducted on the ITT population (Gillings and Koch 1991), which seeks to preserve the benefits of randomization and avoid selection bias. Patients will be analyzed according to the treatment to which they were randomized. In addition, the analyses of primary and key secondary endpoints will be repeated using the PPS population.

Safety population: The safety population is defined as all randomized patients who receive at least 1 dose of investigational product and who did not discontinue from the study for the reason 'Lost to Follow-up' at the first postbaseline visit.

Safety analyses will be performed using the safety population. Patients will be analyzed according to the treatment regimen to which they were assigned. Analyses of the safety endpoints, many of which are incidence based, will include all patients in the safety population, unless specifically stated otherwise.

In the rare situation where a patient is Lost to Follow-up at the first postbaseline visit, but some safety data exists (e.g., unscheduled laboratory assessments) after first dose of study drug, a listing of the data or a patient profile will be provided, when requested.

6.2.2. Definition of Baseline and Postbaseline Measures

The baseline value for efficacy and health outcomes variables measured at scheduled visits is defined as the last non-missing measurement on or prior to the date of first study drug administration (expected at Week 0, Visit 2).

The baseline value for the daily diary assessments (Itch NRS, ADSS, Skin Pain NRS, PGI-S-AD) and for the actigraphy analyses period is the mean of the non-missing assessments in the 7 days prior to the date of first study drug administration (expected at Week 0, Visit 2).

If there are less than 4 non-missing assessments in the baseline diary window, the interval lower bound can be extended up to 7 additional days, one day at a time, to obtain the most recent 4 non-missing values. If there are not at least 4 non-missing assessments in the baseline period, the baseline mean is missing.

The baseline value for actigraphy assessments is the mean of the non-missing assessments in the 7 days prior to the date and time of first study drug administration. The baseline mean for actigraphy variables require there be at least 4 non-missing measurements occurring in at least 4 separate 24-hour increments in the 7 days prior to the date and time of first study drug administration. If this condition is not satisfied, an expanded window of up to 14 days (336 hours) prior to first study drug administration may be utilized in order to obtain the most recent 4 non-missing measurements, occurring in 4 separate 24-hour increments. If there are not at least 4 non-missing assessments collected in the baseline period, the baseline mean will be designated

as missing. Other definitions of baseline value, such as the last measurement on or prior to rescue, may be used to conduct additional supporting analyses.

Baseline for the safety analyses is defined as the last non-missing scheduled (planned) measurement on or prior to the date of first study drug administration for continuous measures by-visit analyses and non-missing measurements on or prior to the date of first study drug administration for all other analyses.

Postbaseline measurements are collected after study drug administration through Week 16 (Visit 8) or early discontinuation visit. Efficacy data collected at scheduled visits (e.g., eCOA, ClinRO) will be used in all analyses unless it is missing. If an assessment is missing at a scheduled visit, an unscheduled post-baseline assessment can be used provided it falls within the window interval as follows: a ± 2 day window is used for Visit 3 (Week 1), Visit 4 (Week 2), and Visit 5 (Week 4); and a ± 4 day window is used to Visit 6 (Week 8), Visit 7 (Week 12), and Visit 8 (Week 16). If there is more than 1 unscheduled visit within the defined visit window and no scheduled visit assessment is available, the unscheduled visit closest to the scheduled visit date will be used. If two unscheduled visits of equal distance are available, then the latter of the two will be used.

Postbaseline daily diary endpoints will be the mean of weekly visit windows (diary windows) anchored on day of first dose (Day 1) and day of Week 16 scheduled visit. Weeks 1-14 are defined as follows:

Week	Days
1	1-7
2	8-14
3	15-21
4	22-28
5	29-35
6	36-42
7	43-49
8	50-56
9	57-63
10	64-70
11	71-77
12	78-84
13	85-91
14	92-98

The Week 16 diary window is the 7 days prior to the scheduled Week 16 visit. If there is no Week 16 scheduled visit, the 7 days prior to the last visit (whether scheduled or unscheduled) occurring after Day 105 constitutes the Week 16 diary window if one exists. If there is no visit on which to anchor the Week 16 diary window, the Week 16 interval and its associated mean are defined as missing. If there are less than 4 non-missing assessments in the Week 16 diary window, the interval can be extended up to 7 additional days, one at a time, to obtain the most recent 4 non-missing values. The assessment of whether 4 non-missing values exist in the Week 16 diary window, and subsequent extension of that window, does not consider censored data in window construction (i.e., they are counted as non-missing unless they are truly unobserved). If the Week 16 diary window has less than 4 non-missing values after extending the Week 16 diary window up to a maximum of 14 days, the Week 16 diary window is defined as 7 days and the mean of the window is missing.

The lower bound of Week 15 diary window is defined as Day 99. The upper bound of the Week 15 diary window is the minimum of either Day 105 or the lower bound of the Week 16 diary window -1. Consequently, Week 15 may be less than 4 days if the Week 16 scheduled visit is before Day 112. Moreover, as Week 15 diary window cannot exceed 7 days, there could be daily assessments between Weeks 15 and 16 diary windows that do not fall into a diary window. If after constructing the diary windows, there are fewer than 4 non-missing values the mean for that particular window is missing and subject to imputation rules.

The postbaseline value of the actigraphy analyses will be analyzed similarly through Week 4 (Visit 5) or early discontinuation but will include time. Thus, Week 1 will be the mean of the 7 days of actigraphy events which has a start date and time occurring within 168 hours of the date and time of first study drug administration. The Week 2, Week 3 and Week 4 scores will be similarly defined. If there are less than 4 non-missing assessments occurring in at least 4 separate 24-hour increments, the weekly interval will be missing. Furthermore, as some analyses require use of the primary censoring rule, assessments collected on the day of rescue or afterwards will be excluded from the weekly visit interval calculation when implementing the rule for daily diary and actigraphy analyses. If, after exclusion of these records, there are less than 4 non-missing assessments, the weekly interval which implements the primary censoring rule will be missing. The post-study follow-up weekly score for daily diaries will be calculated as the mean of the 7 days prior to the follow-up visit which occur after last dose of study treatment.

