- b The symptom-directed physical examination may be repeated at the investigator's discretion any time a patient presents with physical complaints.
- c A posterior–anterior chest x-ray will be performed at screening unless one has been performed within the past 6 months and the x-ray and reports are available.
- d TB test(s) including PPD, QuantiFERON®-TB Gold, and T SPOT®. See Exclusion Criterion [38] for description of TB testing. In countries where the QuantiFERON-TB Gold test or T-SPOT is available, either test may be used instead of the PPD TB test. The QuantiFERON-TB Gold test may be performed locally or centrally; the T-SPOT must be performed locally. (Note: Exception: Patients with a history of active or latent TB who have documented evidence of appropriate treatment, have no history of re-exposure since their treatment was completed, and have a screening chest x-ray with no evidence of active TB may be enrolled if other entry criteria are met. Such patients would not be required to undergo the protocol-specific TB testing but must have a chest x-ray at screening.)
- e If PPD testing was chosen to test for TB, then the patient must return and PPD test read 48 to 72 hours after Visit 1 (post-PPD).
- f Actigraphy devices and ePRO devices will need to be collected from screen fail patients.
- g For patients not entering Study JAHN, their JAHL patient diary will continue to be dispensed at the final visit and returned at Visit 801.
- h Only required if patient met rescue criteria.
- i The following measures (POEM, DLQI, PGI-S-AD, Itch NRS, Skin Pain NRS, ADSS, EQ-5D-5L, WPAI-AD) should be completed prior to any clinical assessments being performed on days when study visits occur.
- j Suicidal ideation and behavior subscales excerpt – Adapted for the assessment of 11 preferred ideation and behavior categories.
- k The Self-Harm Follow-up Form is only required if triggered by the Self-Harm Supplement Form.
- l Clinical chemistry will include the following value calculated by the central laboratory from serum creatinine: estimated glomerular filtration rate (eGFR, calculated using the Chronic Kidney Disease Epidemiology Collaboration [CKD-EPI] Creatinine 2009 equation).
- m Fasting lipid profile: Patients should not eat or drink anything except water for 12 hours prior to sample collection. If a patient attends these visits in a nonfasting state, this will not be considered a protocol violation.

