### **5.1.2. Period 2: Double Blind Placebo-Controlled Treatment**

At Visit 2 (Week 0, baseline), study eligibility for each patient will be reviewed, based on all inclusion and exclusion criteria (Section 6), and laboratory test results. Patients who meet all criteria will proceed to randomization and begin the 16-week double-blind, placebo-controlled treatment period.

At Visit 2, after laboratory samples are collected and all assessments are completed, patients will take the first dose of investigational product at the clinic and pharmacokinetic (PK) samples will be drawn 15 minutes and 1 hour postdose. Pharmacokinetic sampling and the related timing of dosing for investigational product for each visit are detailed in Section 9.5.

Patient will be randomized at a 2:1:1:1 ratio into 1 of the 4 treatment groups (placebo QD, baricitinib 1-mg QD, baricitinib 2-mg QD, or baricitinib 4-mg QD). Investigational product will be administered daily for 16 weeks (treatment period Visits 2 through 8; see Section 7). All patients will be required to use emollients daily. Daily diaries will continue to be utilized throughout the treatment period and through Week 4 for actigraphy devices. Download of this data will be required at study visits. The use of topical corticosteroids (TCS), topical calcineurin inhibitors (TCNIs), crisaborole, and systemic therapies for the treatment of AD are not allowed, except as part of rescue therapy for patients not responding to treatment. Details of rescue therapy and criteria are included in Section 7.7.3. Assessments of disease severity will be performed by the investigator at all study visits including unscheduled and early termination visits (ETVs).

The primary efficacy endpoint and final visit in the treatment period will be at Week 16 (Visit 8). Patients who complete through the Week 16 study visit will be eligible for inclusion in the long-term extension study JAHN (up to 2 additional years of treatment).

If a patient discontinues investigational product for any reason, the patient should remain in the study through Week 16 (Visit 8). If the patient refuses and wishes to withdraw consent, an ETV should be performed as soon as logistically possible.

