#### **9.1.3.2. Itch Numeric Rating Scale**

The Itch Numeric Rating Scale (NRS) is a patient-administered, 11-point horizontal scale anchored at 0 and 10, with 0 representing “no itch” and 10 representing “worst itch imaginable.” Overall severity of a patient’s itching is indicated by selecting the number that best describes the worst level of itching in the past 24 hours (Naegeli et al. 2015; Kimball et al. 2016).

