#### **9.1.3.4. Atopic Dermatitis Sleep Scale**

The Atopic Dermatitis Sleep Scale (ADSS) is a 3-item, patient-administered questionnaire developed to assess the impact of itch on sleep including difficulty falling asleep, frequency of waking, and difficulty getting back to sleep last night. Patient’s rate their difficulty falling asleep and difficulty getting back to sleep, items 1 and 3, respectively, using a 5-point Likert-type scale with response options ranging from 0 “not at all” to 4 “very difficult.” Patients report their frequency of waking last night, item 2, by selecting the number of times they woke up each night, ranging from 0 to 29 times. The ADSS is designed to be completed each day with respondents thinking about sleep “last night.” Each item is scored individually.

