- **H_{4,9,0}:** Mean change from baseline in the score of Item 2 of the ADSS for baricitinib 4-mg patients is greater than or equal to the mean change from baseline in the score of Item 2 of the ADSS for placebo patients at Week 16 [ADSS2 W16]
- **H_{4,10,0}:** Proportion of baricitinib 4-mg patients achieving a 4-point improvement in Itch NRS is less than or equal to the proportion of placebo patients achieving a 4-point improvement in Itch NRS at Week 2 [ITCH W2]
- **H_{4,11,0}:** Mean change from baseline in the score of Item 2 of the ADSS for baricitinib 4-mg patients is greater than or equal to the mean change from baseline in the score of Item 2 of the ADSS for placebo patients at Week 1 [ADSS2 W1]
- **H_{4,12,0}:** Proportion of baricitinib 4-mg patients achieving a 4-point improvement in Itch NRS is less than or equal to the proportion of placebo patients achieving a 4-point improvement in Itch NRS at Week 1 [ITCH W1]
- **H_{2,2,0}:** Proportion of baricitinib 2-mg patients achieving EASI75 is less than or equal to the proportion of placebo patients achieving EASI75 at Week 16 [EASI75]

- **H_{2,3,0}:** Proportion of baricitinib 2-mg patients achieving a 4-point improvement in Itch NRS is less than or equal to the proportion of placebo patients achieving a 4-point improvement in Itch NRS at Week 16 [ITCH W16]
- **H_{2,4,0}:** Percent change from baseline in EASI score for baricitinib 2-mg patients is greater than or equal to the percent change from baseline in EASI score for placebo patients at Week 16 [EASI PCFB]
- **H_{2,5,0}:** Proportion of baricitinib 2-mg patients achieving a 4-point improvement in Itch NRS is less than or equal to the proportion of placebo patients achieving a 4-point improvement in Itch NRS at Week 4 [ITCH W4]
- **H_{2,6,0}:** Proportion of baricitinib 2-mg patients achieving SCORAD75 is less than or equal to the proportion of placebo patients achieving SCORAD75 at Week 16 [SCORAD75]
- **H_{2,7,0}:** Proportion of baricitinib 2-mg patients achieving EASI90 is less than or equal to the proportion of placebo patients achieving EASI90 at Week 16 [EASI90]
- **H_{2,8,0}:** Mean change from baseline in Skin Pain NRS for baricitinib 2-mg patients is greater than or equal to the mean change from baseline in Skin Pain NRS for placebo patients at Week 16 [PAIN W16]

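### The Week 1 ADSS Item 2 mean can include a first-dose-day entry that describes a night before drug, shrinking the estimated effect by one-seventh when that entry is present and the diary is complete

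*SAP*

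**What the plan says.** SAP 6.2.2 states: "Postbaseline daily diary endpoints will be the mean of weekly visit windows (diary windows) anchored on day of first dose (Day 1", and the table that follows gives Week 1 as Days 1-7. The itch-free-days row of SAP Table JAHL.6.6 confirms that Day 1 is the date of first study drug administration. The diary baseline "is the mean of the non-missing assessments in the 7 days prior to the date of first study drug administration", so the dosing-day entry cannot enter baseline and falls in Week 1. A weekly mean needs at least 4 non-missing entries.

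The same SAP section also says: "Postbaseline measurements are collected after study drug administration through Week 16 (Visit 8) or early discontinuation visit".

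On timing, Protocol 5.1.2 says that at Visit 2, "after laboratory samples are collected and all assessments are completed, patients will take the first dose of investigational product at the clinic". Footnote i of the Schedule of Activities (Protocol 2) lists ADSS among the measures that "should be completed prior to any clinical assessments being performed on days when study visits occur". Protocol 9.1.3.4 says "The ADSS is designed to be completed each day with respondents thinking about sleep" on the previous night, and Item 2 counts awakenings in that night.

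SAP 6.6 places the change in ADSS Item 2 at Week 1 in the multiplicity-controlled family for each dose (H4,11,0, H2,11,0 and H1,11,0).

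**The concern.** A Day 1 ADSS entry, at whatever hour it is made, refers to a night that ended before the first tablet. It cannot carry a treatment effect. The window table nevertheless counts it as one of the seven Week 1 days, which conflicts with the SAP's own general sentence on what postbaseline means. No diary rule removes the entry. Actigraphy is handled differently: SAP 6.2.2 starts its Week 1 at the date and time of first dose, so pre-dose data stay out.

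At stake is the size of the estimated early effect on sleep. Week 1 is meant to show early onset, and a pre-dose day in the average makes the estimate systematically smaller than the post-dose effect at each dose. ADSS Items 1 and 3 at Week 1, which are exploratory, share the same window and recall.

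**Working it through.** **The plan's own figure.** The documents give no power, SD or expected effect for Week 1 ADSS Item 2. Their only power statement concerns the primary endpoint. With the Protocol 10.1 inputs (10% vs 30%, two-sided alpha 0.025, 240 vs 120 patients) it reproduces: 99.0% with a pooled-variance test, against a stated figure above 90%. It says nothing about this endpoint.

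**Step 1: complete diary.** Let D be the mean treatment difference over Days 2-7. Under randomisation the expected difference in a pre-dose entry is 0. Then

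Week 1 difference = (1 × 0 + 6 × D) / 7 = 6D/7 = 0.857 D.

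The loss is 1/7 = 14.3%. It is the same at every dose and for any shape of onset across Days 2-7.

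**Step 2: incomplete diary, one patient.** With k entries including Day 1, the Day 1 weight is 1/k: 16.7% for 6 entries, 20% for 5, 25% for 4 (the minimum). It is 0 if Day 1 is missing.

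**Step 3: average over patients.** Assume that each of Days 2-7 is completed independently with probability p, so that J, the number completed, is Binomial(6, p). The values of p are assumptions.

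- Day 1 always completed. Mean weight = E[1/(J+1) | J ≥ 3]. At p = 0.80, the probabilities of J = 6, 5, 4, 3 are 0.262, 0.393, 0.246 and 0.082, which sum to 0.983. Then (0.262/7 + 0.393/6 + 0.246/5 + 0.082/4) / 0.983 = 0.176.
- Day 1 completed at the same rate p. The mean weight is 1/7 by symmetry.
- Day 1 completed by half of patients. Mean weight = 0.5 × E[1/(J+1); J ≥ 3] / [0.5 × P(J ≥ 3) + 0.5 × P(J ≥ 4)]. At p = 0.80: 0.1756 × 0.9830 / (0.9830 + 0.9011) = 0.092.

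| Day 1 completion | p = 0.95 | p = 0.90 | p = 0.80 |
|---|---|---|---|
| Always | 15.0% | 15.8% | 17.6% |
| Same as other days | 14.3% | 14.3% | 14.3% |
| Half of patients | 7.5% | 8.0% | 9.2% |
| Never | 0% | 0% | 0% |

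**Step 4: power, as an illustration only.** Assume unit daily variance, a common correlation ρ between any two days, and adjustment for a 7-day baseline mean. The variance of an n-day mean is V(n) = ρ + (1 − ρ)/n, and the residual variance given baseline is R(n) = V(n) − ρ²/V(7). The signal-to-noise ratio of Days 1-7 relative to Days 2-7 is (6/7) × √[R(6)/R(7)].

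At ρ = 0.6: V(7) = 0.6571, V(6) = 0.6667, R(6) = 0.1188 and R(7) = 0.1093, so the ratio is 0.857 × 1.043 = 0.894. For ρ from 0.4 to 0.8 it runs from 0.895 to 0.893. A nominal 80% at two-sided alpha 0.05 has noncentrality 1.960 + 0.842 = 2.802. Then Φ(2.802 × 0.894 − 1.960) = Φ(0.545) = 0.707, or about 71%.

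**The case against.** The strongest reply is that the SAP's general sentence already limits postbaseline data to those collected after dosing, so a pre-dose entry is excluded and the window table merely groups what remains. That reading is possible, and the documents do not show how the windows are programmed. But the table is explicit that Day 1 belongs to Week 1, and no diary rule says that a Day 1 entry is dropped. The two statements need reconciling in either case.

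A second reply is that one-seventh is not a fixed figure. This stands. Visit-day completion is worded as a recommendation, and the Schedule of Activities has the diary device both returned and dispensed at Visit 2, so Day 1 could be completed less often than other days. That is why the dilution is given as conditional.

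Third, the error is conservative. This also stands: a pre-dose entry pulls the estimate toward zero and cannot create a false positive.

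A reader might infer three stronger things that the documents do not support:

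- *Power falls by one-seventh, or even to 56% from 80%.* One-seventh is a loss in the estimated difference, not in power. The 56% would need a Day 1 SD twice that of the Days 2-7 mean together with a correlation of 1. Under the model in Step 4, an SD ratio near 2 goes with a correlation near 0.2, which gives the 71% above.
- *The Week 1 itch hypotheses are diluted too.* They share the window, but the Itch NRS is answered by "selecting the number that best describes the worst level of itching in the past 24 hours" and no diary hour is fixed. A Day 1 rating could be wholly or partly pre-dose, and a Day 2 rating made within 24 hours of the clinic dose could still reach pre-dose hours. A responder endpoint also does not scale by 1/7.
- *Later weeks are biased as well.* The Week 2, 4 and 16 windows do not contain Day 1, so those means are unaffected.

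**Conclusion.** The point holds for ADSS. Followed as written, SAP 6.2.2 averages any Day 1 ADSS entry, which describes a night before drug, into Week 1. That biases three multiplicity-controlled estimates toward no effect. The size is exactly 14.3% of the Days 2-7 difference when Day 1 is present and the diary is complete. Averaged over patients it ranges from zero to 17.6% across the completion scenarios tabulated above, all of which are assumptions. The result rests on randomisation, which makes the expected Day 1 difference zero, and, for the averages, on completion being unrelated to outcome.

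The power cost cannot be fixed from the documents. The fall from 80% to about 71% is an illustration under an assumed correlation model at alpha 0.05; the local test levels are in Figure JAHL.6.1, which is not shown. Type I error is not inflated, and the primary endpoint is untouched. No itch effect is claimed.

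**What to change.** In SAP 6.2.2, for the ADSS items only, define the Week 1 window as Days 2-7 and require at least 3 non-missing values. Report the Days 1-7 mean as a sensitivity analysis. Leave baseline, all other windows and the itch window unchanged. The change should be settled before unblinding.

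The minimum of 3 matters. A patient evaluable now has at least 4 entries in Days 1-7, hence at least 3 in Days 2-7, so nobody is lost. Requiring 4 of the 6 days would lose 0.2, 1.5 or 8.2 percentage points of patients at an assumed 95%, 90% or 80% daily completion with Day 1 always present.

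The cost is one row or sentence in the window definition and a Week 1 rule for ADSS that differs from the other diary measures. Some Week 1 means will rest on only 3 entries: P(J = 3)/P(J ≥ 3) = 0.2%, 1.5% or 8.3% of evaluable patients at those completion rates. These means are noisier.
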